7.5 Measurements of Treatment Compliance

The level of treatment compliance will be calculated, listed and summarized by treatment group for the mITT population and the safety population for the double-blind treatment phase, the DSP-5423P treatment population for DSP-5423P dosed period and for the open-label population for the open-label treatment phase. Summaries will be repeated by country.

Double-blind treatment phase

- Compliance (percentage) = (actual number of patches applied/ expected number of patches should have been applied) *100.
- Expected number of patches = 2*(the final application date of study medication in the double-blind treatment phase – the initial application date of study medication in the double-blind treatment phase +1) = 2*treatment duration (days).

Open-label treatment phase

- Compliance (percentage) = (actual number of patches applied/ expected number of patches should have been applied) *100.
- Expected number of patches = sum of (number of prescribed patches per day *(start date of each prescription period – end date of each prescription period +1)).
Numbers of 'daily' prescribed patches are 1, 2, and 2 for 40, 60, and 80 mg/day, respectively.

In case of prescription periods are not continuous, ie, there are periods for which no patches are prescribed, these periods are not taken account into calculation.

If any information to calculate the compliance is missing for a subject, then the compliance for the subject is set as missing.

Compliance is considered to have been achieved if the treatment compliance is between 80% and 120%, inclusive. In addition, the following percentage compliance categories will also be presented:

- <80%
- 80 to 120%
- >120%

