##### **The open-label treatment phase**

The investigator or designee will access the IVRS/IWRS at Visit 6, Visits 101~108 (outside Japan), and Visits 101~111 (in Japan) for recording the quantity of the study drug to be dispensed to the subject.

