7.5.1 Extent of Treatment Exposure

Duration of treatment exposure will be calculated and summarized by treatment group for the double-blind treatment phase on the mITT population and the safety population, for the open-label treatment phase on the open-label population, and for the DSP-5423P treatment period on the DSP-5423P dosed population. For the open-label treatment phase and DSP-5423P treatment period, mean daily dose, modal daily dose, last daily dose, Maximum dose, and Cumulative dose will also be presented. Summaries will be repeated by country.

Duration of exposure

Duration of exposure will be calculated for the double-blind treatment phase, open-label treatment phase, and the DSP-5423P treatment period:

- Duration of exposure will be defined in days as the final application date – the initial application date + 1. If either the date is missing, then the duration of exposure will be missing.
- For each treatment phase which is the double-blind treatment phase, open-label treatment phase, or the DSP-5423P treatment period, the initial and final application date corresponding to each phase will be utilized for derivation of duration of exposure. Note that for the DSP-5423P treatment period, and subjects who take placebo in the double-blind treatment phase, initial application date will be a one that DSP-5423P is initially applied.

Statistical Analysis Plan

Version: 2

Study No. D4904020

- Duration of exposures will be summarized in summary statistics as well as the number and percentage of subjects for the following categories.
 - The double-blind treatment phase: 1 to 7 days, 8 to 14 days, 15 to 21 days, 22 to 28 days, 29 to 35 days, 36 days or more
 - The open-label treatment phase: Week 1 to 6*, 7 to 12, 13 to 24, 25 to 36, 37 to 48, 49 or later
 - The DSP-5423P treatment period: Week 1 to 6*, 7 to 12, 13 to 24, 25 to 36, 37 to 48, 49 or later
- *Week 1=Day 1 to 7, Week 2=Day 8 to 14

Mean daily dose

Mean daily dose will be calculated and summarized in summary statistics only for the open-label treatment phase and DSP-5423P treatment period:

- Mean daily dose (mg/day) = total dose of prescribed patches (mg)/duration of exposure (day).
- Total dose of prescribed patches = sum of (total dose of prescribed patches for the prescription period * (start date of the prescription period – end date of the prescription period +1)).

Modal daily dose

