Modal daily dose will be calculated only for the open-label treatment phase and DSP-5423P treatment period:

- Modal daily dose is the most frequently prescribed daily dose during the treatment phase. In the case where there is more than one most frequent dose, eg, both 40 and 60 mg/day are equally frequent then the maximum dose level (eg, 60 mg/day) will be the modal daily dose.
- Modal daily dose will be presented as the number and percentage of subjects for the following categories: 40 mg, 60 mg, 80 mg and Missing

Last daily dose

Last daily dose will be calculated and summarized in summary statistics only for the open-label treatment phase and DSP-5423P treatment period:

- Last daily dose is the prescribed daily dose at the final prescription for the subject during the treatment phase.
- Last daily dose will be presented as the number and percentage of subjects for the following categories: 40 mg, 60 mg, 80 mg and Missing

Maximum dose

Maximum dose will be presented only for the open-label treatment phase and DSP-5423P treatment period:

- Maximum dose is the prescribed daily dose throughout the treatment phase.
- Maximum dose will be presented as the number and percentage of subjects for the following categories: 40 mg, 60 mg, 80 mg and Missing

Cumulative dose

Cumulative dose will be calculated and summarized in summary statistics only for the open-label treatment phase and DSP-5423P treatment period:

- Cumulative dose is Sum of prescribed daily dose x duration of each prescription (days)

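### SAP 7.5 and 7.5.1 count open-label prescription days as start minus end plus 1, so compliance and mean daily dose come out negative for ordinary periods

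*SAP*

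**What the plan says.** SAP 7.5 defines compliance as patches applied over patches expected, times 100. For the open-label phase, expected patches are summed over prescription periods: patches per day (1, 2 and 2 for 40, 60 and 80 mg/day) times a number of days printed as "start date of each prescription period – end date of each prescription period +1". The classification rule is "Compliance is considered to have been achieved if the treatment compliance is between 80% and 120%, inclusive", with further categories below 80% and above 120%.

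SAP 7.5.1 defines mean daily dose as total prescribed dose (mg) over duration of exposure (days), in mg/day. The total dose again uses a reversed count, "start date of the prescription period – end date of the prescription period +1", and its multiplier is worded as a period total: "total dose of prescribed patches for the prescription period * (start date of the prescription period".

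Other SAP formulas run the right way. Double-blind expected patches in 7.5 use final minus initial application date plus 1. In 7.5.1, "Duration of exposure will be defined in days as the final application date – the initial application date + 1". Time to discontinuation in 7.6.2.1.2 follows the same pattern. Cumulative dose, also in 7.5.1, is stated clearly ("Cumulative dose is Sum of prescribed daily dose x duration of each prescription (days").

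**The concern.** The two reversed expressions are derivation rules, and a programmer is meant to code them as printed. Coded literally, they give impossible values: a subject who applied every open-label patch has negative compliance and is tabulated with the non-compliant, and mean daily dose is a negative number of milligrams. Mean daily dose also mixes conventions, because its numerator has the reversed count and its denominator the correct one.

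At stake is the description of exposure and adherence in the long-term phase, which serves the long-term safety and efficacy objective and is repeated by country. If the programmer corrects the formula silently, the tables will be right but will not match the written specification.

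**Working it through.** The documents give no numerical result for these formulas, so there is no figure to reproduce. The check evaluates the formulas directly.

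**Day count.** For a period of n calendar days, end − start = n − 1. The usual count, end − start + 1, gives n. The printed count, start − end + 1, gives −(n − 1) + 1 = 2 − n.

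- n = 1: 1 day (correct by coincidence)
- n = 2: 0 days
- n = 3: −1 day
- n = 7: −5 days
- n = 28: −26 days

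**Inputs.** Patches per day come from SAP 7.5. The lengths of 196 and 364 days are the 28- and 52-week figures in SAP 7.6.2.1.2. The dose course is an assumption: 7 days at 40 mg, 7 at 60 mg, then 80 mg. It follows the 40 mg start until Visit 101 in Protocol 10.1.3 and the 20 mg steps in Protocol 10.2. Every prescribed patch is assumed applied.

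**Main example: 196 days, one period per dose level (7, 7, 182 days).**

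- Expected patches, correct: 1×7 + 2×7 + 2×182 = 385.
- Expected patches, as printed: 1×(−5) + 2×(−5) + 2×(−180) = −375.
- Compliance, as printed: 385 / (−375) × 100 = −102.7%, against 100%.
- Total dose, correct: 40×7 + 60×7 + 80×182 = 15,260 mg; mean 15,260 / 196 = 77.9 mg/day.
- Total dose, as printed (multiplier read as daily dose): 40×(−5) + 60×(−5) + 80×(−180) = −14,900 mg; mean −14,900 / 196 = −76.0 mg/day.

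**Does the result depend on the assumptions?** The alternative split takes one period per dispensing visit. Protocol 9.4 has the dispensing system accessed "at Visit 6, Visits 101~108 (outside Japan), and Visits 101~111 (in Japan) for recording the quantity of the study drug to be dispensed", which gives 9 periods over 196 days (7, 7, 14 and six of 28) and 12 over 364 days in Japan (three more of 56).

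| Assumed course | Periods | Expected patches: printed / correct | Compliance as printed | Mean daily dose: printed / correct (mg/day) |
|---|---|---|---|---|
| 196 days, 40→60→80 mg | 3 | −375 / 385 | −102.7% | −76.0 / 77.9 |
| 196 days, 40→60→80 mg | 9 | −351 / 385 | −109.7% | −71.1 / 77.9 |
| 196 days, 40 mg throughout | 9 | −178 / 196 | −110.1% | −36.3 / 40.0 |
| 364 days, 40→60→80 mg | 3 | −711 / 721 | −101.4% | −77.9 / 78.8 |
| 364 days, 40→60→80 mg | 12 | −675 / 721 | −106.8% | −73.9 / 78.8 |

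The sign is wrong in every row. With the dates in the right order, the way the course is split no longer matters: 385 patches and 77.9 mg/day for both 196-day splits of the titrated course.

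**Short periods.** A single 2-day period gives zero expected patches, so compliance is undefined and mean daily dose is 0. A single 3-day period at 40 mg gives −1 patch and −300%. One day at 40 mg plus two at 60 mg gives 1 expected patch instead of 5, hence 500%.

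**Control.** The double-blind formula gives 2 × 42 = 84 expected patches for 42 days, as it should.

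**The case against.** The best defence is that nobody would be misled. The SAP states the right order several times, negative compliance would show on the first test run, and the outputs are descriptive. All of that stands and caps the severity at minor. It does not make the printed rule correct: the slip appears in two separately worded formulas, and nothing in the SAP overrides them.

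The dose course is assumed, and the split by dispensing visit is only one possibility. Protocol 10.6 has applied patches recorded by dose in the open-label phase, which points towards one period per dose level. This affects the size of the wrong numbers, not their sign for periods of a week or more.

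A reader might infer more than the documents support:

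- *That results are generally zero or undefined.* A zero needs a 2-day period or an exact cancellation. Only compliance can then be undefined; mean daily dose has a correctly ordered denominator and becomes zero or negative.
- *That total dose counts days twice*, since the multiplier is worded as a period total. The SAP's own units exclude this: a period total in mg times days, divided by days, is in mg, whereas the result is declared in mg/day. The cumulative dose definition confirms the daily-dose meaning. A wording repair is enough.
- *That the results hinge on an undefined prescription period.* With the date order corrected, any split into non-overlapping periods covering the same days at the same doses gives the same totals.

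**Conclusion.** The concern holds as a minor drafting error in two formulas. As printed, open-label expected patches, open-label compliance and mean daily dose are negative for ordinary prescription periods of 7 days or longer. In the main example compliance is −102.7% instead of 100% and mean daily dose −76.0 instead of 77.9 mg/day. Those sizes rest on the assumed dose course, full adherence and one period per dose level; the reversal itself follows from the formula alone.

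It would be wrong to infer that any efficacy conclusion is at risk. The per-protocol requirement of at least 80% of treatment in SAP 5.2 concerns the double-blind phase, whose formula is correctly ordered, and the primary analysis uses neither reversed expression. Modal, last and maximum dose do not use the day count, and cumulative dose is defined separately.

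**What to change.** In SAP 7.5 (open-label expected patches) and SAP 7.5.1 (total dose of prescribed patches), replace the day count with end date minus start date plus 1. In 7.5.1, change the multiplier to the prescribed daily dose, so that total dose equals the cumulative dose defined later in the same section.

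The cost is a change of SAP wording, best made before programming. If code already exists, check that these two derivations use the corrected order. Data collection, sample size and the confirmatory analysis are unchanged.

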7.5.1 Extent of Treatment Exposure

Duration of treatment exposure will be calculated and summarized by treatment group for the double-blind treatment phase on the mITT population and the safety population, for the open-label treatment phase on the open-label population, and for the DSP-5423P treatment period on the DSP-5423P dosed population. For the open-label treatment phase and DSP-5423P treatment period, mean daily dose, modal daily dose, last daily dose, Maximum dose, and Cumulative dose will also be presented. Summaries will be repeated by country.

Duration of exposure

Duration of exposure will be calculated for the double-blind treatment phase, open-label treatment phase, and the DSP-5423P treatment period:

- Duration of exposure will be defined in days as the final application date – the initial application date + 1. If either the date is missing, then the duration of exposure will be missing.
- For each treatment phase which is the double-blind treatment phase, open-label treatment phase, or the DSP-5423P treatment period, the initial and final application date corresponding to each phase will be utilized for derivation of duration of exposure. Note that for the DSP-5423P treatment period, and subjects who take placebo in the double-blind treatment phase, initial application date will be a one that DSP-5423P is initially applied.

Statistical Analysis Plan

Version: 2

Study No. D4904020

- Duration of exposures will be summarized in summary statistics as well as the number and percentage of subjects for the following categories.
 - The double-blind treatment phase: 1 to 7 days, 8 to 14 days, 15 to 21 days, 22 to 28 days, 29 to 35 days, 36 days or more
 - The open-label treatment phase: Week 1 to 6*, 7 to 12, 13 to 24, 25 to 36, 37 to 48, 49 or later
 - The DSP-5423P treatment period: Week 1 to 6*, 7 to 12, 13 to 24, 25 to 36, 37 to 48, 49 or later
- *Week 1=Day 1 to 7, Week 2=Day 8 to 14

Mean daily dose

Mean daily dose will be calculated and summarized in summary statistics only for the open-label treatment phase and DSP-5423P treatment period:

- Mean daily dose (mg/day) = total dose of prescribed patches (mg)/duration of exposure (day).
- Total dose of prescribed patches = sum of (total dose of prescribed patches for the prescription period * (start date of the prescription period – end date of the prescription period +1)).

Modal daily dose

Modal daily dose will be calculated only for the open-label treatment phase and DSP-5423P treatment period:

- Modal daily dose is the most frequently prescribed daily dose during the treatment phase. In the case where there is more than one most frequent dose, eg, both 40 and 60 mg/day are equally frequent then the maximum dose level (eg, 60 mg/day) will be the modal daily dose.
- Modal daily dose will be presented as the number and percentage of subjects for the following categories: 40 mg, 60 mg, 80 mg and Missing

Last daily dose

Last daily dose will be calculated and summarized in summary statistics only for the open-label treatment phase and DSP-5423P treatment period:

- Last daily dose is the prescribed daily dose at the final prescription for the subject during the treatment phase.
- Last daily dose will be presented as the number and percentage of subjects for the following categories: 40 mg, 60 mg, 80 mg and Missing

Maximum dose

Maximum dose will be presented only for the open-label treatment phase and DSP-5423P treatment period:

- Maximum dose is the prescribed daily dose throughout the treatment phase.
- Maximum dose will be presented as the number and percentage of subjects for the following categories: 40 mg, 60 mg, 80 mg and Missing

Cumulative dose

Cumulative dose will be calculated and summarized in summary statistics only for the open-label treatment phase and DSP-5423P treatment period:

- Cumulative dose is Sum of prescribed daily dose x duration of each prescription (days)

7.6 Efficacy

Efficacy data will be listed.

7.6.1 Primary Efficacy Analysis

The primary efficacy variable is the mean change in PANSS total score from baseline at Week 6 for testing the superiority of DSP-5423P (40 or 80 mg/day) to placebo in the double-blind treatment phase.

Hypothesis:

Let μ_{40} , μ_{80} , and μ_{placebo} represent the mean changes in PANSS total score from baseline at Week 6 in the DSP-5423P 40 mg group, DSP-5423P 80 mg group, and placebo group, respectively. The following two hypotheses will be tested to compare the mean changes at Week 6 of each DSP-5423P group with that of the placebo group:

- $H_{01}: \mu_{40} = \mu_{\text{placebo}}$ versus the alternate $H_{11}: \mu_{40} \neq \mu_{\text{placebo}}$.
- $H_{02}: \mu_{80} = \mu_{\text{placebo}}$ versus the alternate $H_{12}: \mu_{80} \neq \mu_{\text{placebo}}$.

A mixed model for repeated measurements (MMRM) method will be utilized for the mITT population. The MMRM model will include treatment as a categorical factor, visit (Week 1, 2, 4, and 6; as a categorical factor), pooled study center, baseline PANSS total score as a covariate, and the treatment-by-visit interaction as fixed effects with repeated visits. An unstructured covariance matrix will be used for the within-subject correlation and the Kenward-Rogers approximation will be used to calculate the denominator degree of freedom. In the case of a convergence problem with the unstructured covariance matrix, the following structures with a robust sandwich estimator for the standard error of the fixed effect estimates will be assessed in a sequential fashion: heterogeneous Toeplitz, heterogeneous first-order autoregressive, and Toeplitz. Of the three covariance structures, the first structure yielding convergence will be used for the MMRM analysis. P-values for comparisons of the primary efficacy variable at Week 6 between DSP-5423P groups and the placebo group will be adjusted using the Hochberg procedure (4).

Effect sizes of 40 and 80 mg versus placebo at Week 6 will be calculated as the least square mean of treatment difference divided by square root of the variance estimate, ie, standard deviation (O'Kelly, 2014). Least square means estimates for the treatment difference between the active treatments and placebo treatment at Week 6 will be obtained using the MMRM model. To calculate the standard deviation of change from baseline at Week 6 based on MMRM model, the square root of the variance estimate for that visit, obtained from the SAS-estimated R matrix will be taken (O'Kelly & Ratitch, 2014). The variance estimates for the visits are obtained differently dependent upon the covariance structure being applied for the model. If the MMRM converges using the planned unstructured covariance structure, then the diagonal of the R matrix will be used for variance estimate at each visit. In the case of non-convergence and the use of a heterogeneous Toeplitz based MMRM or first order auto-regressive MMRM then the diagonal cell corresponding to Week 6 from the R matrix can still be used to estimate the variance. However, in the case of non-convergence and the use of a regular Toeplitz based on MMRM, the diagonal from the first column of the R matrix can be used as the variance estimate.

This analysis will be repeated by country and race as well.

The mock SAS code for unstructured covariance model along with codes for the other backup models is provided below:

Initial model:

Statistical Analysis Plan

Version: 2

Study No. D4904020

```
proc mixed data = &ads;  
  class trt01p avisit site usubjid;  
  model chg = trt01p avisit site base trt01p*avisit / DDFM=KR;  
  repeated avisit /type=UN subject=usubjid r;  
  lsmeans trt01p*avisit / diff cl alpha = 0.05;  
  ods output diffs=diffs ;  
  ods output lsmeans = lsmeans;  
  ods output r=r;  
run;
```

In case of non-convergence of the initial model:

```
proc mixed data = &ads empirical  
  class trt01p avisit site usubjid;  
  model chg = trt01p avisit site base trt01p*avisit / DDFM=KR;  
  repeated avisit /type=TOEPH subject=usubjid r;  
  /* repeated avisit /type=ARH(1) subject=usubjid r;*/  
  /* repeated avisit /type=TOEP subject=usubjid r;*/  
  lsmeans trt01p*avisit / diff cl alpha = 0.05;  
  ods output diffs=diffs;  
  ods output lsmeans = lsmeans;  
  ods output r=r;  
run;
```

For adjusted p-value:

```
data a;  
  input Test$ Raw_P @@;  
  datalines;  
  test01 0.28282    test02 0.30688    test03 0.71022;  
  
proc multtest inpvalues=a hoc;  
run;
```

An analysis of sensitivity for the primary efficacy variable will be performed using an analysis of covariance (ANCOVA) model on the mITT population. The response variable for the model will be the change in PANSS total score from baseline at the LOCF endpoint. The ANCOVA model will include treatment as a categorical factor,

pooled study center, and baseline PANSS total score as a covariate. The MMRM and LOCF ANCOVA analysis will also be performed on the PP population to obtain additional information on the robustness of the results.

The mock SAS code for ANCOVA model is provided below:

```
proc mixed data = &ads;  
  class trt01p site;  
  model chg = trt01p site base;  
  lsmeans trt01p / diff cl alpha = 0.05;  
  ods output lsmeans = lsmeans;  
run;
```

In addition to analysis described above, the PANSS total score and change from baseline will be summarized by visit (including LOCF endpoint) and treatment group. Summaries will be repeated for each PANSS item score in same manner, however Wilcoxon signed-rank test for change from baseline to LOCF endpoint within each treatment group will be conducted additionally.

The mock SAS code for Wilcoxon signed-rank test is provided below:

```
proc univariate data = &ads;  
  by visitnum;  
  where trt01p="XXX" ;  
  var chg;  
  output out=XX signrank = signrank;  
run;
```

The estimates of the change from baseline in PANSS total score obtained by the primary analysis model will be plotted by treatment group and visit with +/-SE.

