#### 15.3.5.2 Primary analysis

The primary efficacy variable is the change in PANSS total score from baseline at Week 6 for testing the superiority of DSP-5423P (40 or 80 mg/day) to placebo. A mixed model for repeated measurements (MMRM) method will be used in the mITT population. The MMRM model will include treatment as a categorical factor, visit (Week 1, 2, 4, and 6; as a categorical factor), pooled study center, baseline PANSS total score as a covariate, and the treatment-by-visit interaction. An unstructured covariance matrix will be used for the within-subject correlation and the Kenward-Rogers approximation will be used to calculate the denominator degree of freedom. In case of a convergence problem with the unstructured covariance matrix, the following structures with a robust sandwich estimator for the standard error of the fixed effect estimates will be assessed in a sequential fashion: heterogeneous Toeplitz, heterogeneous first-order autoregressive, and Toeplitz. Of the above three covariance structures, the first covariance structure yielding convergence will be used for the MMRM analysis. P-values for comparisons of the primary efficacy variable at Week 6 between DSP-5423P groups and the placebo group will be adjusted using the Hochberg procedure.

An analysis of sensitivity for the primary efficacy variable will be performed using an

analysis of covariance (ANCOVA) model on the mITT population. The response variable for the model will be the change in PANSS total score from baseline at the LOCF endpoint. The ANCOVA model will include treatment as a categorical factor, pooled study center, and baseline PANSS total score as a covariate. The MMRM and LOCF ANCOVA analysis will also be performed in the PP population to obtain additional information on the robustness of the results.

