2.3 Sample Size and Power

Double-blind treatment phase:

The target number of randomized subjects is 501.

DSP-5423P 40 mg group 167

DSP-5423P 80 mg group 167

Placebo group 167

The sample size for the study was determined by a Monte-Carlo simulation using Statistical Analysis Software (SAS Version 9.3, SAS Institute). The sample size calculation was based on the number of subjects required for the primary analysis in the modified intention-to-treat (mITT) population, where the primary analysis is to be performed on the change in PANSS total score from baseline at Week 6. The Hochberg procedure will be utilized to adjust multiple comparisons between each DSP-5423P (40 and 80 mg/day) group and the placebo group.

Based on the results of a previous double-blind placebo control study using DSP-5423 (1), the effect size was estimated to be 0.650 for DSP-5423 5 mg/day and 0.667 for DSP-5423 10 mg/day. It is expected that changes in PANSS total score will be smaller in the current study. This is due to patients with new exacerbated psychotic state will be enrolled as opposed to only patients hospitalized within two weeks from acute aggravation of schizophrenia in the earlier study. In addition, the drug-placebo differences in schizophrenia have been documented to decrease over time (2). For the reasons noted above, the effect size in the current study is assumed to be 0.45 which is about two-thirds of the effect size of DSP-5423 5 mg/day and DSP-5423 10 mg/day. A sample size of 133 per group was estimated to yield a complete power (probability of rejecting 2 null hypotheses) of 89% with a two-sided 5% significance level using the Hochberg procedure for multiplicity adjustment for two comparisons and taking an interim analysis for futility into consideration. Considering that there is the possibility

of subjects discontinuing before completion of the double-blind treatment phase, the total sample size will need to be 501 subjects or 167 subjects per treatment group.

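### The primary MMRM uses one baseline slope for all four visits; adding baseline-by-visit is a cheap way to gain some Week 6 precision if that slope changes over time

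*SAP*

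**What the plan says.** SAP 7.6.1 fits an MMRM to change from baseline with treatment, "visit (Week 1, 2, 4, and 6; as a categorical factor"), pooled center, "baseline PANSS total score as a covariate, and the treatment-by-visit interaction as fixed effects with repeated visits". The mock code matches: "model chg = trt01p avisit site base trt01p*avisit / DDFM=KR". Protocol 15.3.5.2 gives the same terms ("baseline PANSS total score as a covariate, and the treatment-by-visit interaction"), as does the statistical methods part of the synopsis. For the covariance, "An unstructured covariance matrix will be used for the within-subject correlation", with Kenward-Roger degrees of freedom.

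The only interaction with visit is treatment. The same model is reused for PANSS subscales, five-factor scores and CGI-S (SAP 7.6.2) and for the DIEPSS total (SAP 7.7.2). It is refitted by country and race (SAP 7.6.1, 7.6.4), and the subgroup MMRM in 7.6.4 also has no baseline-by-visit term.

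On power, SAP 2.3 says "the effect size in the current study is assumed to be 0.45" and "A sample size of 133 per group was estimated to yield a complete power (probability of rejecting 2 null hypotheses) of 89" per cent. The documents give no baseline SD, no slope of change on baseline at any visit, and no residual SD by visit.

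**The concern.** The response is a change score, and its relation to baseline need not be the same at Week 1 as at Week 6. The plan itself gives a reason to expect growth. The responder definition in SAP 7.6.2 scales improvement by baseline minus 30. If improvement is roughly proportional to that quantity, the slope of change on baseline is minus the fractional improvement, and it steepens as patients improve. With an assumed mean baseline of 95 (not stated), the tablet-study changes in protocol Table 16 imply endpoint slopes from about −12.213/65 = −0.19 (placebo) to −29.516/65 = −0.45 (10 mg).

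A single slope is a generalized least squares compromise across visits. If early visits are less variable, it sits near the Week 1 slope. Week 6 is then under-adjusted, and the misfit goes into its residual variance. Precision at the one tested visit is at stake. So is the reported effect size, which SAP 7.6.1 divides by the square root of the Week 6 variance from the fitted R matrix.

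**Working it through.** **1. Stated power.** Inputs from SAP 2.3: 133 per group, effect size 0.45, "two-sided 5% significance level using the Hochberg procedure".
- Per comparison: 0.45 × √(133/2) − 1.960 = 3.670 − 1.960 = 1.710, so marginal power is 95.6%.
- Hochberg rejects both hypotheses when both p ≤ 0.05. With correlation 0.5 from the shared placebo arm, complete power is 92.3% without an interim.
- With a half-way futility look at 8% current-trend conditional power, simulation gives 89.6% if either dose falling below 8% stops the study. It gives 89.2% if the rule uses the conditional power of rejecting both, and 92.0% if both doses must fall below 8%. The stated 89% reproduces under the first two rules.
- Table 16's effect sizes come from raw SDs of change. For 5 mg, (−27.123 + 12.213)/22.799 = −0.654, or −0.650 after the small-sample correction. No baseline adjustment enters the 89%.

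**2. Parameter cost.** Four slopes instead of one is three extra fixed effects.

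**3. Excess Week 6 variance under one slope.** In large samples the common slope is b_c = Σ w_j b_j, with w = V⁻¹1 / (1ᵀV⁻¹1) and V the residual covariance. The proportional excess is (b₆ − b_c)² × Var(baseline) / Var(residual at Week 6).

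Assumed, not in the documents: baseline SD 14, Week 6 residual SD 21.5 and the slopes below, equal across arms. The variance ratio is 14²/21.5² = 196/462.25 = 0.424. Three covariance patterns are used:
- A: residual SDs in ratio 0.5/0.7/0.9/1.0, AR(1) 0.75; weights 1.04/−0.08/−0.05/0.09.
- B: the same SDs, exchangeable 0.6; weights 0.96/0.20/−0.05/−0.11.
- C: constant SD, exchangeable; weights 0.25 each.

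| Slopes, Weeks 1/2/4/6 | A: b_c, excess | B: b_c, excess | C: b_c, excess |
|---|---|---|---|
| Equal: −0.25 throughout | −0.250, 0% | −0.250, 0% | −0.250, 0% |
| Mild: −0.15/−0.18/−0.22/−0.25 | −0.153, 0.40% | −0.142, 0.50% | −0.200, 0.11% |
| Moderate: −0.10/−0.18/−0.27/−0.35 | −0.108, 2.49% | −0.080, 3.08% | −0.225, 0.66% |
| Strong: −0.05/−0.20/−0.35/−0.50 | −0.064, 8.06% | −0.016, 9.93% | −0.275, 2.15% |

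Example (strong, A): (−0.50 + 0.064)² × 0.424 = 0.190 × 0.424 = 8.06%, an SE ratio of √1.0806 = 1.040.

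Across baseline SDs of 10 to 18 and residual SDs of 17.5 to 26.8 (the range of raw SDs in Table 16), pattern A gives 0.1–1.0% (mild), 0.8–6.2% (moderate) and 2.7–20% (strong).

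**4. Simulation check** (pattern A, 167 per arm, 300 trials per scenario, pooled center omitted). With complete data the ratio of model SEs, single slope to baseline-by-visit, was 1.000, 1.002, 1.012 and 1.040 for equal, mild, moderate and strong. With about 15% missing-at-random dropout it was 1.000, 1.002, 1.012 and 1.039. With equal slopes the added term gave the smaller SE in only 52% and 51% of trials. Mean error was about 0.1 point with and without the term, against a simulation error of about 2.3/√300 = 0.13.

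**5. In power terms** (no interim, base 92.3%). A variance gain of 0.4% is worth +0.1 point of complete power and 2.5% is worth +0.7. A gain of 8% (133 × 1.08 = 143.6 per group) is worth +2.0.

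**The case against.** The strongest reply is that nothing is broken. Protocol and SAP agree on a pre-specified model, the stated power already ignores baseline adjustment, and the gain rests on slopes that the documents do not give. All of that stands. Four further points have weight.

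- A reader might infer that the extra term always sharpens the Week 6 contrast. It does not: with equal slopes the SE ratio is 1.000.
- A reader might infer that the single-slope model biases the treatment effect, or leaves chance baseline imbalance as a second, separate harm. Under randomization the simulations showed no bias, with or without dropout. The residual imbalance is the same quantity as the excess variance and should not be counted twice.
- The term is not clearly free in small fits. Appendix II lists 21 randomized in Korea and 13 + 15 = 28 in China, over three arms, and each fit already estimates ten covariance parameters.
- Changing the SAP alone would create a discrepancy with the protocol on the primary model. Appendix II lists 582 randomized and SAP 7.6.4 defines the interim set as the first 251, so the interim look has very probably taken place. The change therefore needs documenting as blinded.

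The LOCF ANCOVA in SAP 7.6.1 does fit its own endpoint slope. That covers the point only partly, because it changes the missing-data handling at the same time.

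**Conclusion.** The point holds as an optional but worthwhile efficiency improvement to the full-sample model. The planned analysis is valid, and a reading that it is wrong or that the stated 89% is overstated for this reason is not supported.

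Whether anything is gained depends on an assumption the documents cannot settle: that the baseline slope at Week 6 differs from the pooled slope. At baseline SD 14 and residual SD 21.5, the excess Week 6 variance is 0% with equal slopes, under 1% with mild growth, roughly 1 to 3% with moderate growth and 2 to 10% with strong growth. Under pattern A that is at most about 4% of the SE and 2 points of complete power. Only the extreme corner of the wider grid (baseline SD 18, residual SD 17.5, strong growth) reaches 20%. The reported effect size would shrink by the same factor as the SE ratio. Against this, no material precision was lost when the slopes were equal.

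**What to change.** Before the double-blind data are unblinded, add `base*avisit` to the MODEL statement of the primary MMRM and of the full-sample PANSS subscale, five-factor, CGI-S and DIEPSS MMRMs that reuse it. Evaluate LS means at the mean baseline. Make the same change in the synopsis and section 15.3.5.2 of the protocol. Record it in SAP section 8, which now lists no changes, with a statement that those deciding had no access to unblinded interim results. Keep the single-slope model for the by-country, by-race and subgroup fits, and say so.

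The cost is three fixed-effect parameters and a documented amendment; no new data are needed. If the sponsor prefers not to alter the primary model this late, the same term can be pre-specified as a sensitivity analysis. That would show whether the slope matters but would not bring the precision into the primary test.
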